- AEs of CTCAE grade 3 or higher by SOC and PT
- AEs assessed by investigator as possibly related to study treatment by SOC and PT
- AEs assessed by investigator as possibly related to study treatment by SOC, PT and maximum reported CTCAE grade.
- Time to onset of first AE (days) by SOC and PT
- Duration of first AE (days) by SOC and PT
- AEs leading to hospitalisation by SOC and PT
- AEs by PT and maximum reported CTCAE grade

- AEs by PT and relationship to study treatment
- AEs with outcome death by SOC and PT
- AEs assessed by investigator as possibly related with outcome death by SOC and PT
- SAEs by SOC and PT
- SAEs leading to discontinuation of study treatment by SOC and PT
- SAEs leading to discontinuation of study treatment assessed by investigator as possibly related to study treatment by SOC and PT
- Non-serious AEs sorted by decreasing frequency by PT.
- SAEs assessed by investigator as possibly related to study treatment by SOC and PT
- AEs leading to discontinuation of study treatment by SOC and PT
- AEs assessed by investigator as possibly related to study treatment leading to discontinuation of study treatment by SOC and PT
- AEs leading to reduction of study treatment by SOC and PT
- AEs leading to interruption of study treatment by SOC and PT

For patients with multiple AEs of the same SOC and/or PT, only the AE with the highest CTCAE grade per system organ class and preferred term will be included in the summaries presented by maximum CTCAE grade. Similarly, for multiple AEs differing in causality, only the AE with causality will be included in by-causality summaries. If causality is missing, the AE will be considered related in all summaries.

In summaries including SOC or PT, the summaries are sorted by international order for SOC and in alphabetical order for PT.

The following summaries for the number and percentage of patients will be created for AESIs if applicable:

- By PT
- By outcome
- By time of resolution
 - On-treatment, which is defined as AEs with onset date on or after first study treatment, but before or on date of end of treatment;
 - Follow-up, which is defined as AEs with onset after, but within 28 days after end of treatment;
 - Post-treatment, which is defined as AEs with onset after 28 days after end of treatment.

4.14.5 Deaths

A summary will be provided with the number and percentage of patients who died, and death event was categorised as:

- AEs with outcome of death only
- Related to disease under investigation only
- Both related to disease under investigation and an AE with outcome of death only
- AEs with a start date after 28 days after treatment discontinuation with an outcome of death
- Other deaths

A corresponding listing will also be produced.

4.14.6 Clinical Laboratory Evaluation

All local laboratory results collected will be listed according to the SoA in Tables 14, 15 and Tables 21, 22 in the study protocol.

Summaries for safety laboratory will include the parameters as specified in [Table 1](#) and [Table 2](#).

Table 1 Laboratory Safety Variables - Clinical Chemistry

Albumin	Cholesterol ^a	Magnesium
Alkaline phosphatase	C-reactive protein	Phosphate
Alanine aminotransferase	Creatinine	Potassium
Amylase ^b	Gamma-glutamyl transferase	Sodium
Aspartate aminotransferase	Glucose ^a	Triglycerides ^a
Bicarbonate	Glutamate dehydrogenase	Total protein
Bilirubin (total and direct)	Lactate dehydrogenase	Chloride
Blood urea nitrogen	Lipase ^b	Uric acid
Corrected calcium		

^a Fasting cholesterol, triglyceride and glucose values are not required. However, if non-fasting values are abnormal, a repeat sample should be obtained when the patient is fasting.

^b Collected at screening, pre-infusion on each dosing day, and end of treatment visit.

Table 2 Laboratory Safety Variables - Haematology

Absolute leucocyte differential count: neutrophils, lymphocytes, monocytes, basophils, eosinophils	CCI
Blood (B)-haemoglobin	Haematocrit
Leucocytes	Platelet count

All values will be classified as low (below normal range), normal (within normal range), or high (above normal range) based on local laboratory normal reference ranges. Results will be converted to standard units. For assessments included in CTCAE version 5.0, the CTCAE grade will be determined.

All clinical laboratory results will be listed.

For all continuous laboratory assessments, the absolute values and the change from baseline will be summarised using descriptive statistics at each time point by dose level/cohort as appropriate.

For clinical chemistry and haematology, shift tables from baseline to worst on-treatment value according to reference range classification will be created. CTCAE grade changes from baseline to the maximum on-treatment grade will also be provided. Corresponding shift tables ("Negative", "Trace", "Positive", "0", "+", "++", "+++") will be produced for urinalysis

Liver biochemistry test results over time for patients with elevated ALT or AST ($\geq 3 \times$ ULN) and elevated bilirubin ($\geq 2 \times$ ULN,) regardless of whether or not these elevations occurred at the same visit, or ALT or AST of $\geq 5 \times$ ULN, will be tabulated and plotted.

All parameters as used for summaries including amylase and lipase, coagulation indices, serum immunoglobulins, urinalysis, cardiac troponin and BNP (or NTproBNP), clinical and laboratory assessments for TLS, Cortisol, ACTH and TSH parameters will be listed as appropriate.

Following SRC review of emerging data additional laboratory safety assessment sample times may be added or removed if indicated by the emerging data. For presentation of the results this analysis plan will follow the initial time schedule for these parameters.

4.14.7 Vital Signs

The following vital signs will be assessed and listed:

- Systolic blood pressure (SBP) [mmHg]
- Diastolic blood pressure (DBP) [mmHg]
- Pulse rate (bpm)
- Oral body temperature (°C)
- Respiration rate (breaths/min)
- Body weight (kg)

Change from baseline in vital signs variables will be calculated for each post-dose visit.

Descriptive statistics for absolute values and changes from baseline will be presented by dose level/cohort as appropriate.

Blood pressure and pulse rate will be plotted as subject profiles.

4.14.8 ECGs

The following parameters will be assessed in 12-lead ECGs:

- PR-interval (msec).
- QRS-duration (msec).
- QT-interval (msec).
- QT-interval corrected using the Fridericia correction formula (QTcF) (msec).
- RR-interval (msec).
- Heart rate (beats per minute [bpm]).

The ECG will be evaluated by the Investigator as 'Normal', 'Abnormal'.

All ECG parameters will be listed by patient including changes from baseline for numeric ECG parameters.

Descriptive statistics for the means of the triplicate ECG measurements in absolute values and changes from baseline will be presented by dose level/cohort as appropriate. The values used for this summary are the average of the three measurements of the triplicate ECG.

A shift table for the overall ECG assessment from baseline to the worst (abnormal) on-treatment assessment will be created.

Subject profiles will be plotted for the means of the triplicate ECG measurements in absolute values.

QTcF outliers (defined as values following study treatment that are greater than 470 msec or increases from baseline greater than 30 msec) will be summarised using cumulative counts and percentages under the following categories:

- Absolute value > 470 msec

- Absolute value > 480 msec
- Absolute value > 500 msec
- Change from baseline > 30 msec
- Change from baseline > 60 msec
- Absolute value > 470 msec and change from baseline > 30 msec
- Absolute value > 500 msec and change from baseline > 60 msec.

4.14.9 LVEF

Descriptive statistics for left ventricular ejection fraction (LVEF) for absolute values and changes from baseline will be presented by dose level/cohort as appropriate.

Summary tabulations of frequencies will be presented for:

- Baseline CTCAE grade, as defined by:
 - $\geq 50\%$ (CTCAE Grade 0)
 - 40% to $< 50\%$ (CTCAE grade 2)
 - 20% to $< 50\%$ (CTCAE grade 3)
 - $< 20\%$ (CTCAE grade 4).
- Maximum on-treatment CTCAE grade, as defined by:
 - $\geq 50\%$ (CTCAE Grade 0)
 - 40% to $< 50\%$ or 10 to 19% drop from baseline (CTCAE grade 2)
 - 20% to $< 50\%$ or 20 to 29% drop from baseline (CTCAE grade 3)
 - $< 20\%$ (CTCAE grade 4).

In addition, the results of (echocardiograms [ECHO] / multi-gated acquisition scan [MUGA]) scans for LVEF will be listed.

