- 9 White blood cell count must be $< 10 \times 10^9/L$ prior to the first dose in Cycle 1, Day 1. Treatment with hydroxyurea (AML) or high-dose steroids (ALL and leukaemia of ambiguous lineage) during screening and Cycle 1 to control white blood cell count is permitted. Both medications can be started or stopped at any point during this period.
- 10 Adequate organ function at screening defined in [Table 3](#):

Table 3 Organ Function Parameters

Category	Parameter	Value
Hepatic	Total bilirubin	$\leq 1.5 \times \text{ULN}$
		$\leq 3 \times \text{ULN}$ in presence of Gilbert's syndrome
	AST and ALT	$\leq 2.5 \times \text{ULN}$
Coagulation	INR	$< 1.5 \times \text{ULN}$
Pancreatic	Lipase	$\leq 1.5 \times \text{ULN}$
	Amylase	$\leq 1.5 \times \text{ULN}$ and absence of clinical pancreatitis
Renal*	Serum creatinine	$\leq 1.5 \times \text{ULN}$
	CrCl by Cockcroft and Gault method: $\text{CrCl (mL/min)} = \frac{(140 - \text{age [years]}) \times \text{weight (kg)} \times (F)}{(72 \times \text{serum creatinine mg/dL})}$ ^a where F = 0.85 for females and F = 1 for males	$\geq 50 \text{ mL/min}$

*For patients with below ideal body weight, the 24-hour urine test may be used: ideal body weight (kg) = constant + 0.91 (height [cm] - 152.4); constant is 50 for men and 45.5 for women.

ALT, alanine transaminase; AST, aspartate transaminase; CrCl, creatinine clearance; INR, international normalised ratio; ULN, upper limit normal.

- 11 Adequate cardiac function as demonstrated by left ventricular ejection fraction (LVEF) $> 50\%$ on screening cardiac multigated acquisition (MUGA), magnetic resonance imaging (MRI), or echocardiogram (ECHO).

- 12 Willing and able to participate in all required study evaluations and procedures including receiving IV administration of study treatment and admission to the hospital, when required, for administration of study treatment and monitoring.
- 13 All patients must consent to and undergo both pretreatment and on-treatment fresh bone marrow aspirates and biopsies
- 14 For inclusion in the genetic component of the study, patients must fulfil the following additional criteria:
 - Provision of signed, written, and dated informed consent for genetic research. If a patient declines to participate in the genetic component of the study, there will be no penalty or loss of benefit to the patient. The patient will not be excluded from other aspects of the study described in this protocol, as long as they consented to the main study.

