Baseline will generally be the last value obtained prior to the first dose of study medication. Alternatively, if two visits are equally eligible to assess patient status at baseline (e.g. screening and baseline assessments both on the same date prior to first dose), the average will be taken as a baseline value. In the scenario where there are two assessments pre-dose on day 1, one with time recorded and the other without time recorded, the one with time recorded will be selected as the baseline value. Where safety data are summarized over time, study day will be calculated in relation to date of first dose.

For assessments performed on the day of first dose for which time is not captured a nominal pre-dose indicator as the variable label will serve as evidence that the assessment occurred prior to first dose. Assessments on the day of first dose where neither time nor a nominal pre-dose indicator are captured will be considered prior to first dose if such procedures are required by the protocol to be conducted before first dose.

Change from baseline will be calculated as the post-dose value minus the baseline value as:

$$\text{post-baseline value} - \text{baseline value}$$

Percent change from baseline will be calculated as:

$$\frac{\text{post-baseline value} - \text{baseline value}}{\text{baseline value}} \times 100\%$$

For considerations for analysis of pharmacokinetic data refer to sections 4.13.1, and 4.13.2.

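### SAP 4.14.9: the LVEF Grade 2 and Grade 3 bands overlap at 40 to <50% and the Grade 3 drop criterion stops at 29%, so the maximum on-treatment grade table can misgrade patients if coded as written

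*SAP*

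**What the plan says.** SAP 4.14.9 plans descriptive statistics for LVEF and its change from baseline, a listing of the scan results, and two frequency tables of grade.

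- The first table, introduced by "Baseline CTCAE grade, as defined by", uses absolute LVEF only: Grade 0 at 50% or more, Grade 2 at 40 to <50%, Grade 3 at 20 to <50%, Grade 4 below 20%.
- The second, introduced by "Maximum on-treatment CTCAE grade, as defined by", keeps the same absolute bands and adds a drop criterion to the two middle grades: "40% to $< 50\%$ or 10 to 19% drop from baseline (CTCAE grade 2" and "20% to $< 50\%$ or 20 to 29% drop from baseline (CTCAE grade 3".

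The section does not say whether the drop is in percentage points or relative to baseline, and has no rule for a value that meets two bands. SAP 4.2 fixes the reference value: "Baseline will generally be the last value obtained prior to the first dose of study medication". SAP 8.12.9 sends Module 1 Part A to this section, and SAP 4.2 has summaries presented by dose level or cohort. Protocol 5.1 requires "Adequate cardiac function as demonstrated by left ventricular ejection fraction (LVEF" above 50% at screening.

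**The concern.** An ordered toxicity scale should give each patient one grade, and a larger fall should never receive a lower grade than a smaller one. These bands break both conditions. The 40 to <50% range belongs to two grades. The drop criterion has a ceiling, so a patient can pass beyond Grade 3 on drop and return to Grade 0 while LVEF remains at or above 50%.

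What is at stake is the worst-grade LVEF table by dose level in Module 1 Part A. LVEF is among the safety assessments listed in SAP 3.2.3 and 7.2.3, and a row labelled CTCAE Grade 3 will be read as a severe cardiac finding. Protocol 11.1.3.2 plans at least 3 DLT-evaluable patients and allows up to 12 patients at a dose level. One misgraded patient is then 1/12 = 8% to 1/3 = 33% of the level.

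**Working it through.** The plan has no figure to reproduce here, so the check applies the printed rule literally.

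**Inputs.** The bands are from SAP 4.14.9 and entry LVEF above 50% is from Protocol 5.1. I tried every whole-number pair with baseline 51 to 90% and on-treatment LVEF from 5% up to baseline, which is 2660 pairs. The limits of 90% and 5% are my assumptions. The counts are grid cells, not expected patients.

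**Rule as written.** Grade = the highest grade whose absolute or drop criterion is met. Drop in points = baseline − value; relative drop = 100 × (baseline − value) / baseline.

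**Comparison rule.** Grade 2 = 40 to <50% or a drop of 10 to <20; Grade 3 = 20 to <40% or a drop of 20 or more; Grade 4 below 20%; take the worse.

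**Worked cases.** Where one grade is shown, it holds under both readings of the drop.

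| Baseline → value | Points | Relative | As written | Exclusive bands |
|---|---|---|---|---|
| 55 → 48 | 7 | 12.7% | 3 | 2 |
| 55 → 45 | 10 | 18.2% | 3 | 2 |
| 65 → 45 | 20 | 30.8% | 3 | 3 |
| 70 → 40 | 30 | 42.9% | 3 | 3 |
| 82 → 57 | 25 | 30.5% | 3 (points), 0 (relative) | 3 |
| 82 → 51 | 31 | 37.8% | 0 | 3 |

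**Overlap.** All ten whole numbers from 40 to 49 meet Grades 2 and 3. With the higher grade taken, Grade 2 can arise only from a 10 to 19% drop with LVEF still at or above 50%. There are 40 × 10 = 400 pairs with an on-treatment value of 40 to 49. In points, 135 move from Grade 3 to Grade 2 under exclusive bands and 400 − 135 = 265 stay Grade 3 because the drop is 20 or more. In relative percent, 51 move.

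**Drop ceiling.** The affected patients have a drop of at least 30 and LVEF of at least 50%.

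- Points: baseline ≥ 50 + 30 = 80%. Of 1460 pairs with a drop of 30 or more, 1394 reach Grade 3 or 4 through the absolute band and 66 are Grade 0.
- Relative: 0.70 × baseline ≥ 50, so baseline ≥ 50 / 0.70 = 71.4%, or 72% in whole numbers. Of 1796 such pairs, 138 are Grade 0.

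The reversal appears under either reading. From a baseline of 82%, a fall to 57% (25 points) is Grade 3 and a fall to 51% (31 points) is Grade 0. In relative terms, a fall to 60% is 22/82 = 26.8%, Grade 3, and a fall to 57% is 30.5%, Grade 0.

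**Small gap.** Drops between 19 and 20 meet neither drop criterion. From 70% to 50.5% is 19.5 points and is Grade 0 in points.

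**The two defects interact.** If only the overlap were removed, then in points 75 → 45 (a drop of 30) would become Grade 2 while 70 → 45 (a drop of 25) stayed Grade 3. Both edits are needed.

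**The case against.** The strongest reply is that the text does not force a wrong table. *Maximum* may mean the worst grade across visits, not the higher of two bands met at one visit, and a programmer assigning bands in listed order would put 40 to <50% in Grade 2. That stands as a reason to make the statement conditional. It does not remove the defect, because two reasonable programs would give different tables and the SAP does not choose between them.

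Several stronger readings are tempting, and the documents do not support them.

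- *Drops of 30 or more are left ungraded.* They are not. The absolute bands cover every LVEF value, and none of the 2660 pairs is without a grade. Only those with LVEF still at or above 50% are under-graded, as Grade 0.
- *Every patient whose worst value is 40 to <50% is wrongly moved to Grade 3.* Those with a drop of 20 or more are Grade 3 under exclusive bands too.
- *DLT or discontinuation decisions are affected.* Protocol 6.6.5 and 11.4.7.2 rest on cardiac events assessed by the investigator, not on this table, and SAP 4.14.3 places MTD evaluation outside this analysis.
- *A primary endpoint is misstated.* LVEF is not named among the endpoints in SAP 2.1; it is one of the supporting safety assessments.

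It is also fair that the baseline overlap is largely moot, since entry requires LVEF above 50% and Protocol 11.6.2.7 schedules only the screening scan before dosing.

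**Conclusion.** The derivation rule is faulty in two places, but the reach is limited. If both bands are applied and the higher grade is taken, an on-treatment value of 40 to <50% with a drop under 20 is tabulated as Grade 3 instead of Grade 2. A drop of 30 or more with LVEF still at or above 50% is tabulated as Grade 0, below the grade given to a drop of 20 to 29; this needs a high baseline, about 80% in points or about 72% in relative terms.

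The maximum on-treatment LVEF grade table by dose level can therefore be wrong, if it is coded as written and a patient falls in these ranges. How many patients do so cannot be known from the documents. Descriptive statistics and listings of LVEF remain correct.

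The conclusion rests on one inference: that Grade 3 was meant to be 20 to <40%. The SAP's own neighbours imply it, because Grade 2 starts at 40% and Grade 4 lies below 20%. The CTCAE text is not among the documents.

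**What to change.** In SAP 4.14.9:

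1. Make the tabulation bands mutually exclusive in both lists by setting the absolute Grade 3 band to 20 to <40%.
2. In the on-treatment list, set the Grade 2 drop to 10 to <20 and leave the Grade 3 drop open-ended at 20 or more. This also closes the gaps at 19 to 20 and 29 to 30.
3. Define the drop as percentage points or as relative percent of baseline.
4. State that the grade at each assessment is the worse of the absolute and drop criteria, and that the table shows the worst on-treatment assessment.

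The cost is a few lines of SAP wording and one derivation. No new data are needed.

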4.14.10 Eastern Cooperative Oncology Group Performance Status (ECOG PS)

ECOG performance status scores will be assessed at screening and before each dose of AZD0466 according to ECOG criteria as follows:

- 0 = Fully active, able to carry out all pre-disease activities without restrictions
- 1 = Restricted in physically strenuous activity but ambulatory and able to carry out work of a light or sedentary nature, e.g. light housework, office work
- 2 = Ambulatory and capable of self-care, but unable to carry out any work activities. Up and about more than 50% of waking hours
- 3 = Capable of only limited self-care, confined to bed or chair more than 50% of waking hours
- 4 = Completely disabled, cannot carry on self-care, totally confined to bed or chair
- 5 = Death.

The ECOG performance status will be listed and summarised as frequency counts by dose level/cohort and visit as appropriate.

4.14.11 Tumour lysis syndrome (TLS)

Table of key subject information for patients with tumour lysis syndrome will be provided. This listing will comprise

- Disease history (AML/ALL), age, gender, cohort
- Baseline risk of TLS as specified in Table 3
- WBC, LDH, BUN at baseline
- Allopurinol, and Rasburicase prophylaxis (identified by ATC-code list from prior or concomitant medications)
- Date and time of TLS assessment
- Parameters contributing to the laboratory TLS
- Parameters contributing to the clinical TLS with Cairo-Bishop Grade
- Overall Cairo-Bishop Grade (as assessed by the investigator)
- AE term and number, AE recorded as a DLT, AE serious, AE start and stop dates, and AE outcome.

Table 3 Risk of tumour lysis syndrome

Malignancy	Risk of tumour lysis syndrome ^a		
	High	Intermediate	Low
Acute myeloid leukaemia	WBC $\geq 100 \times 10^9/L$	WBC ≥ 25 and $\leq 100 \times 10^9/L$ or WBC $< 25 \times 10^9/L$ and LDH $\geq 2x$ ULN	WBC $< 25 \times 10^9/L$ and LDH $< 2x$ ULN
Acute lymphoblastic leukaemia	WBC $\geq 100 \times 10^9/L$ and LDH $\geq 2x$ ULN	WBC $< 100 \times 10^9/L$ and LDH $< 2x$ ULN	-

^a WBC $< 10 \times 10^9/L$ is required for study eligibility and hydroxyurea is permitted during screening and Cycle 1 to achieve this; consequently patients will be intermediate or low risk of TLS.

Risk classification adapted from MD Anderson Cancer Center guidance.

Summary tabulations of frequencies for Overall Cairo-Bishop Grade (as assessed by the investigator) will be presented at patient- and event-level for:

- Laboratory TLS
- Clinical TLS
- Cairo-Bishop TLS Grade
- TLS classified as a DLT

Time to first onset of Laboratory TLS and Time to first onset of Clinical TLS will be presented as categorical groupings by cycle, and as summary statistics, including Kaplan-Meier statistics (Q1, median and Q3).

4.14.12 Determination of Sample Size

Refer to the individual modules.

4.14.13 Interim Analyses

Refer to the individual modules.

5 INTRODUCTION – Module 1 Part A

Module 1 will evaluate the safety, tolerability, PK, and efficacy of AZD0466 as monotherapy. Part A is a dose escalation assessment of the safety and tolerability of AZD0466 to determine the recommended dose and schedule for further evaluation.

As Module 1 Part B was not initiated, Sections 6, 7 and 8 describe the analyses to be conducted for Module 1 Part A.

For further general study information refer to Section 1.

6 STUDY OBJECTIVES - Module 1 Part A

The core objectives and endpoints for the study are listed in Sections 2.1, 2.2, and 2.3; additional endpoints for Module 1 Part A are listed in Sections 6.1, 6.2, and 6.3.

6.1 Primary Objective

Objectives	Endpoints/Variables
To assess the safety and tolerability of AZD0466 in patients with advanced haematological malignancies	DLT MTD RP2D and schedule

DLT, dose-limiting toxicity; MTD, maximum tolerated dose; RP2D, recommended Phase II dose

